5.2 Laboratory Evaluations

The following laboratory tests will be performed at all scheduled visits 1-4:

HEMATOLOGY: hemoglobin, hematocrit, red blood cell count, white blood cell count, % neutrophils, % lymphocytes, % monocytes, % basophils, % eosinophils, absolute neutrophils, absolute lymphocytes, absolute monocytes, absolute basophils, absolute eosinophils, platelet count

CHEMISTRY: sodium, potassium, chloride, carbon dioxide, blood urea nitrogen (BUN), creatinine, glucose, calcium, phosphorus, albumin, total protein, uric acid, total bilirubin, direct bilirubin, indirect bilirubin, alkaline phosphatase, alanine aminotransferase, (ALT, SGPT), aspartate aminotransferase (AST, SGOT), creatine phosphokinase, lactate dehydrogenase

URINALYSIS: pH, specific gravity, blood, glucose, ketones, microscopic exam (RBC and WBC, only when indicated), leukocyte esterase, protein

Urine pregnancy test will be performed at Visit 1 only.

For hematology, chemistry and urinalysis actual values and changes from baseline will be summarized descriptively by visit and treatment group, as well as both treatment group combined.

Additionally, numeric hematology, chemistry and urinalysis results will be classified as Low (below the reference range), Normal (within the reference range) or High (above the reference range). Categorical urinalysis results will be classified as Normal or Abnormal. Shifts among these categories between baseline and last available post-baseline assessment will be provided.

All results will be listed.

Additionally, subject listings will be provided for the following occurrences during the trial:

1. Liver enzyme (ALT or AST) values \geq 2.5 times the upper limit of normal;
2. Serum creatinine level \geq 1.75 times the upper limit of normal.

For subjects/tests that meet the above criteria at least once during the study, results from all available visits will be shown.

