2 GENERAL CONSIDERATIONS FOR DATA ANALYSIS

The database will be locked and final analysis of the data will be performed after all subjects have completed the study, outstanding data queries have been resolved or adjudicated as unresolvable, and the data have been cleaned and finalized. The statistical analyses will be performed by Quartesian LLC, with approval of the Sponsor, using SAS Version 9.4 (or higher).

All tables, figures and listings will be produced in landscape format.

Subjects will be assigned to treatment group defined by the treatment the subject received in the double-blind phase of the previous study IPX203-B16-02 (IPX203 or IR CD-LD).

In general, all data will be listed by subject and visit/time point where appropriate. The summary tables will be stratified by, or have columns corresponding to, treatment groups. Total group will also be presented.

The total number of subjects in the treatment group (N) under the stated population will be displayed in the header of summary tables.

Data will be summarized using descriptive statistics for continuous variables. Unless otherwise specified, descriptive statistics will include number of subjects, mean, standard deviation, minimum, median and maximum. Number of subjects with missing values will also be displayed, but only if non-zero. The minimum and maximum statistics will be presented to the same number of decimal places as the original data. The mean and median will be presented to one more decimal place than the original data. The standard deviation will be presented to two more decimal places than the original data.

In summary tables of categorical variables, counts and percentages will be displayed. The count [n] indicates the actual number of subjects in a particular category, which should always be less than or equal to the total number of subjects

in the respective study group with known (non-missing) category [M]. Percentage will be obtained by: % = n/M*100. Unless otherwise specified, all percentages will be expressed to one decimal place.

In by-visit summaries, only data collected on scheduled visits/timepoints will be summarized. Data from unscheduled assessments will be included in listings and may be used in determination of baseline if applicable.

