5.3 Vital Signs

Vital signs will be collected at all scheduled visits. Blood pressure, heart rate and respiratory rate will be collected at all visits, temperature at Visits 1 and 4 only. Blood pressure and heart rate will be recorded at two positions: supine and standing.

Weight will also be measured at all scheduled visits.

Vital signs (including weight) and their changes from baseline will be summarized descriptively by visit, position and treatment group, as well as for both treatment groups combined.

Vital signs will also be classified as follows:

- Systolic blood pressure: < 90 mmHg, 90 to < 140 mmHg, and \geq 140 mmHg.
- Diastolic blood pressure: < 60 mmHg, 60 to < 90 mmHg, and \geq 90 mmHg.
- Heart rate: < 60 beats/min, 60 to < 100 beats/min, and \geq 100 beats/min.
- Respiratory rate: < 9 breaths/min, 9 to < 20 breaths/min, \geq 20 breaths/min.
- Body temperature < 36.5°C, 36.5°C to < 37.5°C, 37.5°C to < 38.5°C, and \geq 38.5 °C

Subjects will be summarized with counts and percentages by these categories.

Orthostatic hypotension is defined as a systolic blood pressure decrease of \geq 20 mmHg or a diastolic blood pressure decrease of \geq 10 mmHg within 3 minutes of standing.

Number and percentage of subjects with orthostatic hypotension will be presented by treatment group and visit, as well as at least once after baseline.

All vital signs will be listed.

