5.4 Electrocardiogram

ECG will be performed at all scheduled visits 1-4. The following parameters will be recorded: Ventricular Rate (beats/min), PR Interval (msec), QRS Duration (msec), QT Interval (msec), RR Interval (msec), Rhythm Assessment (Normal Sinus Rhythm VR 60-100 bpm, Sinus Bradycardia VR less than 60 bpm, Sinus Tachycardia VR greater than 100 bpm or Other) and Overall Interpretation (Normal, Abnormal Not Clinically Significant (NCS) or Abnormal Clinically Significant (CS)).

QT Interval corrected using Fridericia's formula (QTcF) will be calculated as follows:

$$QTcF = \frac{QT}{\sqrt[3]{\left(\frac{RR}{1000}\right)}}$$

Ventricular rate and ECG intervals will be summarized descriptively with their changes from baseline by visit and treatment group as well as for both treatment groups combined.

Rhythm assessment and overall interpretation will be summarized categorically by visit and treatment group, as well as both treatment group combined.

Shifts in overall interpretation from baseline to the last available post-baseline assessment will be tabulated.

Additionally, ECG parameters will be classified as follows:

| Parameter | Categories of value | Categories of change from baseline |
|------------------|---|--|
| Ventricular rate | < 60 beats/min, 60 to 100 beats/min, and > 100 beats/min | < -10 beats/min, -10 to < 0 beats/min, 0 to < 10 beats/min, and \geq 10 beats/min. |
| PR Interval | < 120 msec, 120 to 200 msec, and > 200 msec | < -1 msec, -1 to 5 msec, and \geq 5 msec |
| QRS Interval | < 60 msec, 60 to 100 msec, and > 100 msec | < 0 msec, 0 to < 3 msec, and \geq 3 msec |
| QT Interval | < 200 msec, 200 to 430 msec, >430 to 450 msec, >450 to 500 msec, and > 500 msec | < 30 msec, 30 to < 60 msec, and \geq 60 msec |
| RR Interval | < 600 msec, 600 to 1000 msec, and > 1000 msec | < -33 msec, -33 to < 12 msec, and \geq 12 msec |
| QTcF Interval | < 200 msec, 200 to 430 msec, > 430 to 450 msec, > 450 to 500 msec, and > 500 msec | < 30 msec, 30 to < 60 msec, and \geq 60 msec |

Subjects will be summarized by number and percentage in each of the categories above by visit and treatment group, as well as both treatment group combined.

All results will be listed.

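### Laboratory and ECG shift tables stop at the last post-baseline value, and QTcF categories are counted only visit by visit, so no planned laboratory or ECG table gives the number of subjects who were ever abnormal after baseline

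*SAP*

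**What the plan says.** **Laboratory tests (SAP 5.2).** The by-visit tables hold values and changes: "For hematology, chemistry and urinalysis actual values and changes from baseline will be summarized descriptively by visit and treatment group". Low/Normal/High (numeric tests) and Normal/Abnormal (categorical urinalysis) are used only in the shift table: "Shifts among these categories between baseline and last available post-baseline assessment will be provided". All results are listed. Extra listings cover ALT or AST at 2.5 times the upper limit of normal or more, and creatinine at 1.75 times or more: "For subjects/tests that meet the above criteria at least once during the study, results from all available visits will be shown".

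**ECG (SAP 5.4).** "Shifts in overall interpretation from baseline to the last available post-baseline assessment will be tabulated". Interpretation also appears visit by visit: "Rhythm assessment and overall interpretation will be summarized categorically by visit and treatment group". The value and change categories, including QTcF, follow the same layout: "Subjects will be summarized by number and percentage in each of the categories above by visit and treatment group".

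**Orthostatic hypotension (SAP 5.3).** Here the plan adds a per-subject count over the whole study: "Number and percentage of subjects with orthostatic hypotension will be presented by treatment group and visit, as well as at least once after baseline".

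**Unscheduled data.** SAP 2 states: "In by-visit summaries, only data collected on scheduled visits/timepoints will be summarized". SAP 2.3 lets an unscheduled value replace a missing scheduled one within 14 days either side of the planned date. SAP 6 maps laboratory samples and ECGs taken outside regular visits because of COVID-19 to the closest visit.

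**The concern.** The objective is long-term safety, and protocol 13.6 has laboratory tests and ECGs evaluated over the whole course of the study. A basic safety question is how many subjects became abnormal at any time. A baseline-to-last table answers a different question: how many were abnormal at the end.

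The difference could matter here because investigators may adjust the IPX203 regimen (protocol 6.5) and PD co-medication may be changed or started (protocol 9.2.1). An abnormality that leads to a change may have resolved by the last assessment, and the shift table would then show nothing.

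For QTcF the loss is smaller. A value above 500 msec at a scheduled visit is counted in that visit's table. But visit counts cannot be combined into a number of subjects.

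**Working it through.** The plan states no rate on this point, so there is no figure to reproduce. The check has two parts: following a case through the tables, and an illustration of size.

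**1. Where a transient abnormality appears**

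| Finding at Month 3, resolved by the last assessment | By-visit table | Shift table | Count of subjects ever affected |
|---|---|---|---|
| Numeric laboratory test out of range, Normal at baseline | Contributes to mean, minimum or maximum; not counted as abnormal | Normal to Normal | None |
| ECG interpretation abnormal, Normal at baseline | Counted at Month 3 | Normal to Normal | None |
| QTcF above 500 msec, or change of 60 msec or more | Counted at Month 3 | Not applicable | None |
| Orthostatic hypotension | Counted at Month 3 | Not applicable | Planned |

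For categorical urinalysis, the by-visit summary of actual values may show result counts, but the Normal/Abnormal class is still used only in the shift.

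**2. Why visit counts do not give a subject count.** Suppose 3, 3 and 3 subjects have QTcF above 500 msec at Visits 2, 3 and 4. The number of distinct subjects lies between max(3, 3, 3) = 3 and 3 + 3 + 3 = 9.

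**3. Illustration of size for a last-value table**

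Inputs:
- Three post-baseline visits (SAP 1.2) and about 300 subjects (SAP 1.3).
- Assumed: p = 5% abnormal at each visit, all subjects Normal at baseline, no dropout.

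*Independent visits.* P(ever) = 1 − (1 − 0.05)³ = 14.3%. In 300 subjects, 42.8 are ever abnormal and 300 × 0.05 = 15.0 are abnormal at the last visit. Captured: 5/14.3 = 35%.

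*Correlated visits (beta-binomial).* With intraclass correlation ρ, set m = (1 − ρ)/ρ and b = 0.95m. Then P(ever) = 1 − [b/m] × [(b + 1)/(m + 1)] × [(b + 2)/(m + 2)]. For ρ = 0.5, m = 1 and b = 0.95, so P(ever) = 1 − 0.95 × 0.975 × 0.9833 = 8.9%.

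| ρ | P(ever abnormal) | Captured by last value |
|---|---|---|
| 0 | 14.3% | 35% |
| 0.3 | 10.8% | 46% |
| 0.5 | 8.9% | 56% |
| 0.75 | 6.9% | 73% |
| 0.9 | 5.7% | 87% |

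*Second model (two-state Markov chain).* Let r be the chance of staying abnormal from one visit to the next, and q = p(1 − r)/(1 − p). Then P(ever) = 1 − (1 − p)(1 − q)². At p = 5% the share missed is 59.5% (r = 0.25), 49.7% (r = 0.5), 33.2% (r = 0.75) and 16.6% (r = 0.9). The lesson is the same: persistence sets the size, while the direction is always an under-count.

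**The case against.** The strongest reply is that little is hidden. Every laboratory and ECG result is listed. ALT, AST and creatinine have listings triggered by a single qualifying value. By-visit tables meet the protocol synopsis's promise of summaries at each time point. The adverse event definition in protocol 12.2.1 includes abnormal laboratory findings, and SAP 5.1 counts a subject once per preferred term whenever the event began on treatment, resolved or not. The study is descriptive and nonrandomized, so a worst-value table could be added at reporting without endangering any inference.

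Most of this stands, and it limits the point. It does not remove it: listings are not rates, the special listings cover three analytes, and adverse event reporting depends on the investigator's judgement.

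A reader might also infer four stronger things that the documents do not support:

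- **That transient ECG or QTcF abnormalities vanish from the tables.** Those at scheduled visits are counted at that visit. Only the count of distinct subjects is missing.
- **That anyone High in mid-study and Normal at the end is shown as unchanged.** This is true only if baseline was Normal. A subject High at baseline would show as High to Normal.
- **That unscheduled values are excluded throughout.** The exclusion in SAP 2 concerns by-visit summaries. SAP 2.3 and SAP 6 bring some in, and the SAP does not say whether an unscheduled value can be the last available one for a shift.
- **That the last-value table would capture only about a third to a half of affected subjects.** That needs weak to moderate persistence, which nothing in the documents establishes.

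**Conclusion.** The point holds in limited form. No laboratory or ECG table counts subjects who were ever abnormal after baseline. The gap is widest for laboratory tests, where an out-of-range value that returns to normal by the last assessment enters no table as Low or High. For ECG interpretation and QTcF, what is missing is the per-subject count across visits.

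On an assumed 5% rate per visit, a last-value table would capture about 35% of ever-abnormal subjects with independent visits and about 87% at an intraclass correlation of 0.9. The rate, the correlations, the absence of dropout and the Normal baseline are all assumptions, and this capture range does not apply to QTcF, which is tabulated at every visit. No section of the SAP explains why orthostatic hypotension gets an ever-after-baseline count and these measures do not. SAP 7 defers whole-exposure adverse event, vital sign and ECG summaries to the Integrated Summary of Safety; it does not mention laboratory data or promise a worst-value analysis. This is a cheap improvement, not a threat to the study's conclusions.

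**What to change.** Keep the last-value shifts and add the following:

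1. **SAP 5.2:** shifts from baseline to the worst post-baseline value, with lowest and highest shown separately for two-sided numeric tests, and to any Abnormal result for categorical urinalysis.
2. **SAP 5.4:** a shift from baseline to the worst post-baseline overall interpretation, ordered Normal, Abnormal NCS, Abnormal CS.
3. **SAP 5.4:** an ever-after-baseline row for the QTcF value and change categories, following the SAP 5.3 treatment of orthostatic hypotension.
4. **Data rule:** state that these tables use all scheduled and unscheduled post-baseline values up to the Visit 4/ET assessment. A defined end point is needed because the SAP sets no on-treatment window for laboratory tests or ECGs. State also whether unscheduled values may serve as the last available assessment in the existing shifts.

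The cost is a few sentences and a few tables from data already collected, and SAP 1 leaves room for the change before database lock. Worst-value rates are higher by construction than single-visit rates, so the tables must be labelled as such and not compared with last-value or by-visit percentages.

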5.3 Vital Signs

Vital signs will be collected at all scheduled visits. Blood pressure, heart rate and respiratory rate will be collected at all visits, temperature at Visits 1 and 4 only. Blood pressure and heart rate will be recorded at two positions: supine and standing.

Weight will also be measured at all scheduled visits.

Vital signs (including weight) and their changes from baseline will be summarized descriptively by visit, position and treatment group, as well as for both treatment groups combined.

Vital signs will also be classified as follows:

- Systolic blood pressure: < 90 mmHg, 90 to < 140 mmHg, and \geq 140 mmHg.
- Diastolic blood pressure: < 60 mmHg, 60 to < 90 mmHg, and \geq 90 mmHg.
- Heart rate: < 60 beats/min, 60 to < 100 beats/min, and \geq 100 beats/min.
- Respiratory rate: < 9 breaths/min, 9 to < 20 breaths/min, \geq 20 breaths/min.
- Body temperature < 36.5°C, 36.5°C to < 37.5°C, 37.5°C to < 38.5°C, and \geq 38.5 °C

Subjects will be summarized with counts and percentages by these categories.

Orthostatic hypotension is defined as a systolic blood pressure decrease of \geq 20 mmHg or a diastolic blood pressure decrease of \geq 10 mmHg within 3 minutes of standing.

Number and percentage of subjects with orthostatic hypotension will be presented by treatment group and visit, as well as at least once after baseline.

All vital signs will be listed.

5.4 Electrocardiogram

ECG will be performed at all scheduled visits 1-4. The following parameters will be recorded: Ventricular Rate (beats/min), PR Interval (msec), QRS Duration (msec), QT Interval (msec), RR Interval (msec), Rhythm Assessment (Normal Sinus Rhythm VR 60-100 bpm, Sinus Bradycardia VR less than 60 bpm, Sinus Tachycardia VR greater than 100 bpm or Other) and Overall Interpretation (Normal, Abnormal Not Clinically Significant (NCS) or Abnormal Clinically Significant (CS)).

QT Interval corrected using Fridericia's formula (QTcF) will be calculated as follows:

$$QTcF = \frac{QT}{\sqrt[3]{\left(\frac{RR}{1000}\right)}}$$

Ventricular rate and ECG intervals will be summarized descriptively with their changes from baseline by visit and treatment group as well as for both treatment groups combined.

Rhythm assessment and overall interpretation will be summarized categorically by visit and treatment group, as well as both treatment group combined.

Shifts in overall interpretation from baseline to the last available post-baseline assessment will be tabulated.

Additionally, ECG parameters will be classified as follows:

| Parameter | Categories of value | Categories of change from baseline |
|------------------|---|--|
| Ventricular rate | < 60 beats/min, 60 to 100 beats/min, and > 100 beats/min | < -10 beats/min, -10 to < 0 beats/min, 0 to < 10 beats/min, and \geq 10 beats/min. |
| PR Interval | < 120 msec, 120 to 200 msec, and > 200 msec | < -1 msec, -1 to 5 msec, and \geq 5 msec |
| QRS Interval | < 60 msec, 60 to 100 msec, and > 100 msec | < 0 msec, 0 to < 3 msec, and \geq 3 msec |
| QT Interval | < 200 msec, 200 to 430 msec, >430 to 450 msec, >450 to 500 msec, and > 500 msec | < 30 msec, 30 to < 60 msec, and \geq 60 msec |
| RR Interval | < 600 msec, 600 to 1000 msec, and > 1000 msec | < -33 msec, -33 to < 12 msec, and \geq 12 msec |
| QTcF Interval | < 200 msec, 200 to 430 msec, > 430 to 450 msec, > 450 to 500 msec, and > 500 msec | < 30 msec, 30 to < 60 msec, and \geq 60 msec |

Subjects will be summarized by number and percentage in each of the categories above by visit and treatment group, as well as both treatment group combined.

All results will be listed.

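### SAP 5.4: the PR change categories overlap at exactly 5 ms, and the PR, QRS and RR change limits are unexplained and too narrow to mark out unusual subjects

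*SAP*

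**What the plan says.** SAP 5.4 classifies each ECG parameter twice, by value and by change from baseline. The change categories are:

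- PR: "< -1 msec, -1 to 5 msec", then 5 ms or more.
- QRS: "< 0 msec, 0 to < 3 msec", then 3 ms or more.
- RR: "< -33 msec, -33 to < 12 msec", then 12 ms or more.
- Ventricular rate: "< -10 beats/min, -10 to < 0 beats/min, 0 to < 10 beats/min", then 10 beats/min or more.
- QT and QTcF: "< 30 msec, 30 to < 60 msec", then 60 ms or more.

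On reporting, the section states: "Subjects will be summarized by number and percentage in each of the categories above by visit and treatment group", and for both groups combined. SAP 2 computes each percentage as the category count over the number of subjects with a known category.

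The value categories are conventional bands, for PR "< 120 msec, 120 to 200 msec, and > 200 msec". The SAP gives no rationale for the PR, QRS and RR change limits. Neither document gives the variability of any ECG interval.

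**The concern.** Two things look wrong. First, the PR row is not a partition. Its middle category has no strict upper bound, and the next category starts at the same number. A programmer must either count some subjects twice or adopt a reading that the SAP does not state.

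Second, the PR, QRS and RR change limits are only a few milliseconds for PR and QRS and a few beats per minute for RR. For QRS, any decrease at all leaves the middle band. If ordinary visit-to-visit variation carries most subjects across these limits, the counts say little about which subjects had a notable change.

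Long-term safety is part of the study objective. SAP 7 postpones the ECG summary over all IPX203 exposure to the Integrated Summary of Safety, so these are the ECG change tables that this study's report will carry. All subjects receive IPX203 (Protocol 6.3), so there is no concurrent control against which to judge how often the limits are crossed without the drug.

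**Working it through.** The plan states no figure on this point, so there is none to reproduce.

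**1. Overlaps and gaps.** Every whole-number change from -300 to +300 was checked against each change row, and every value from 0 to 1999 against the value rows. The only value in more than one category is a PR change of 5 ms. There are no gaps. The ventricular rate, QRS, QT, RR and QTcF change rows all use half-open bands.

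**2. Size of the double count.** Assumptions: no drug effect, change distributed Normal(0, SD), recording in whole ms. The SDs are assumed.

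P(change = 5) = Φ(5.5/SD) − Φ(4.5/SD)

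- SD 8 ms: 4.1%, or about 12 of 300 subjects; the PR column sums to 104.1%.
- SD 16 ms: 2.4%, or about 7 of 300; the column sums to 102.4%.
- Wider range, SD 5 to 20 ms: 4.8% down to 1.9%.

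The 300 is the approximate enrolment in SAP 1.3 and serves only as a scale.

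**3. RR against ventricular rate.** This uses only the SAP's limits and RR (ms) = 60000 / rate. The value bands agree exactly: 60000/1000 = 60 and 60000/600 = 100 beats/min. The change bands do not.

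| Baseline rate (beats/min) | RR (ms) | RR −33 ms, as rate change | RR +12 ms, as rate change | +10 beats/min, as RR change (ms) | −10 beats/min, as RR change (ms) |
|---|---|---|---|---|---|
| 60 | 1000 | +2.1 | −0.7 | −143 | +200 |
| 70 | 857 | +2.8 | −1.0 | −107 | +143 |
| 80 | 750 | +3.7 | −1.3 | −83 | +107 |
| 100 | 600 | +5.8 | −2.0 | −55 | +67 |

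At 70 beats/min, for example, 60000/(857 + 12) = 69.0. That subject is in the top RR change category and in an inner ventricular-rate category on the same ECG.

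**4. Share outside the middle band with no drug effect.** Same model. With lower limit L and upper limit U:

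below = Φ((L − 0.5)/SD); above = 1 − Φ((U − 0.5)/SD)

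A PR change of 5 ms is counted as above. Sums may differ in the last digit through rounding.

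| Interval (L, U) | Assumed SD (ms) | Below | Above | Outside |
|---|---|---|---|---|
| PR (−1, 5) | 5 | 38.2% | 18.4% | 56.6% |
| PR | 10 | 44.0% | 32.6% | 76.7% |
| PR | 20 | 47.0% | 41.1% | 88.1% |
| QRS (0, 3) | 3 | 43.4% | 20.2% | 63.6% |
| QRS | 5 | 46.0% | 30.9% | 76.9% |
| QRS | 10 | 48.0% | 40.1% | 88.1% |
| RR (−33, 12) | 40 | 20.1% | 38.7% | 58.8% |
| RR | 80 | 33.8% | 44.3% | 78.1% |
| RR | 120 | 39.0% | 46.2% | 85.2% |

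**5. Would a real shift still show?** For PR with SD 10 ms, the share with a change of 5 ms or more is 33% with no shift, 52% with a mean shift of +5 ms and 71% with +10 ms. The counts do move with a true shift.

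**The case against.** The strongest reply is that the overlap is a missing strict-inequality sign in one row. The other change rows point to that reading, and where the SAP wants overlapping groups it says so, as for the concomitant-medication subgroups in SAP 5.1. This is probably right. It makes the slip easy to correct but does not remove it from the text that will be programmed.

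A second reply is that the SAP nowhere calls the outer bands outliers or clinically significant. Finer RR bands do not contradict coarser rate bands, and the rate row itself has a cut at zero. This stands in part: the difference is one of scale, not a logical contradiction. But the value bands for RR and rate match exactly, and no reason is given for change bands of the same quantity that differ several-fold.

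A reader might infer that the ECG tables in general count subjects twice. They do not: the overlap is confined to PR change, at one value. A reader might also infer that the tables cannot show a drug effect. That does not follow. Step 5 shows that a mean shift moves the counts. SAP 5.4 also plans continuous summaries of every interval and its change, value categories, QT and QTcF change at 30 and 60 ms, a shift table for overall interpretation, and full listings. Attribution to the drug is limited by the uncontrolled design whatever limits are used.

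Finally, the limits may match those of the preceding study, whose plan is not available here. That would be a reason to state, and the SAP does not state it.

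**Conclusion.** The point holds, and it is minor. The PR overlap at 5 ms is certain from the text. Its effect, if programmed literally, is about 2% to 4% of subjects counted twice per visit. That figure rests on assumed change SDs of 8 to 16 ms and 1 ms recording; the documents give neither the SD nor the recording resolution.

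The mismatch between the RR change limits (about 1 to 6 beats/min at rates of 60 to 100) and the outer 10 beats/min limits follows from the SAP's own numbers. That the PR, QRS and RR limits leave more than half of subjects outside the middle band with no drug effect rests on assumed SDs, but it held at every SD tried: 57% to 88% for PR, 64% to 88% for QRS and 59% to 85% for RR.

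The supportable conclusion is that these three change tables flag many subjects without clinical meaning. No test, error rate or sample size is affected.

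**What to change.** Amend the SAP 5.4 table before database lock:

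1. Make the PR middle category run from −1 to strictly below 5 ms. The three PR categories are then exclusive and exhaustive, and the percentages sum to 100%.
2. Align the RR change limits with the 10 beats/min rate limits, or drop the RR change categories as redundant with ventricular rate. Because the millisecond equivalent of 10 beats/min depends on the baseline rate (step 3), dropping them is the simpler course.
3. State the reason for the PR and QRS change limits, or replace them with pre-specified outlier criteria tied to the table's own value limits. Examples are a new PR above 200 ms or a new QRS above 100 ms after a baseline within limits.

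This is a table and programming edit that needs no new data. The cost is the loss of direct comparability with any earlier tables that used the present limits.
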